### STATISTICAL MODELS

Difference between groups will be tested for variables stated below. Independent T-test or Mann-Whitney U-test will be used for continuous variables depending on if the data has a normal or skewed distribution. Fishers's exact test will be used for categorical variables.

### Covariates to test (possible confounding factors):

- Energy\_kcal\_EP\_3 (total energy intake at endpoint, categorized in tertiles)
- Sum\_satured\_fat\_EP\_3 (sum of saturated fats (g) at endpoint, categorized in tertiles)
- Fat\_fish\_group\_EP (categorized intake of fat fish at endpoint)
- Calcium\_EP\_3 (intake of calcium at endpoint, categorized in tertiles)
- Physical\_activity\_BL\_group (categorized physical activity at baseline)
- f47\_1\_EP (changed physical activity during intervention)
- Biopsies\_cancer (percent of biopsies with cancer at diagnosis)
- gleason\_cat (categorized Gleason score at diagnosis)
- gleason\_cat\_rp (categorized Gleason score at surgery)
- rp\_teritargradjanej (categorized tertiary Gleason degree at surgery)
- Age\_inclusion (continuous age at baseline)
- BMI\_group (BMI at baseline in groups)
- Weight\_diff (difference in weight between endpoint and baseline)
- smoking (categorized smoking at baseline)
- heredity (categorized heredity at baseline)
- Zinc\_EP\_3 (intake of zinc at endpoint, categorized in tertiles)
- Alcohol\_EP\_3 (intake of alcohol at endpoint, categorized in tertiles)
- Sum\_monosat\_fat\_EP\_3 (intake of monounsaturated fatty acids at endpoint, categorized in tertiles)
- Sum\_polysat\_fat\_EP\_3 (intake of polyunsaturated fatty acids at endpoint, categorized in tertiles)
- red\_meat\_EP\_3 (intake of red meat at endpoint, categorized in tertiles)
- vegetables\_all\_EP\_3 (intake of vegetables at endpoint, categorized in tertiles)
- fruit\_all\_EP\_3 (intake of fruits at endpoint, categorized in tertiles)
- Vit\_E\_EP\_3 (intake of vitamin E at endpoint, categorized in tertiles)

• Finasteride (intake of Finasteride under intervention, no=0, yes=1)

Pearson or Spearman correlation coefficient will be used to evaluate whether dietary covariates are correlated. If the correlation coefficient between two covariates in the model or between covariates and the main exposure are higher than 0.6, multicolinearity issues is considered, eventually one of the covariates will be excluded from the model.

Model building:

The association between intake of phytoestrogens and tumor proliferation will evaluated by regression models, providing estimate of risk difference (RD) relative risk (RR) and corresponding 95% confidence intervals.

Crude models:

C0: Ki-67

C1: C0 + Group\_intervention C2: C0 + Phytoestogens\_EP C3: C0 + Isoflavones\_EP C4: C0 + Lignans\_EP C5: C0 + Coumestrol\_N58\_EP

C02: PSA\_total\_diff C12: C02 + Group\_intervention C22: C02 + Phytoestogens\_EP C32: C02 + Isoflavones\_EP C42: C02 + Lignans\_EP C52: C02 + Coumestrol N58 EP

C03: PSA\_ratio\_diff C13: C03 + Group\_intervention C33: C03 + Phytoestogens\_EP C43: C03 + Isoflavones\_EP C53: C03 + Lignans\_EP C63: C03 + Coumestrol N58 EP

C04: estradiol\_diff\_cat C14: C04 + Group\_intervention C34: C04 + Phytoestogens EP C44: C04 + Isoflavones\_EP C54: C04 + Lignans\_EP C64: C04 + Coumestrol N58 EP

C05: testo\_diff\_cat C15: C05 + Group\_intervention C35: C05 + Phytoestogens\_EP C45: C05 + Isoflavones\_EP C55: C05 + Lignans\_EP C65: C05 + Coumestrol\_N58\_EP

 $\underline{C0_6:} testo_estrad_ratio_diff$   $C1_6: C0_6 + Group\_intervention$   $C3_6: C0_6 + Phytoestogens\_EP$   $C4_6: C0_6 + Isoflavones\_EP$   $C5_6: C0_6 + Lignans\_EP$   $C6_6: C0_6 + Coumestrol\_N58\_EP$ 

C07: testo\_SHBG\_ratio\_diff C17: C07 + Group\_intervention C37: C07 + Phytoestogens\_EP C47: C07 + Isoflavones\_EP C57: C07 + Lignans\_EP C67: C07 + Coumestrol\_N58\_EP

Final model:

Which covariates included in the model will be based on:

- 1) If a known risk factor for the outcome (based on previous subject matter knowledge and with the help of Directed Acyclic Graphs)
- 2) If differs between groups of exposure
- 3) proportional ( $\geq 10\%$ ) change in  $\beta$ -coefficients

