### INCLUSION CRITERIA

- Patients with prostate cancer T1–T2, Gleason score <8, prostate-specific antigen (PSA) <20
- scheduled for radical prostatectomy.

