### Definition of secondary outcomes

Levels of PSA are analyzed from blood samples taken at the inclusion meeting (baseline) and in connection with another visit within one week before surgery (endpoint). The difference is calculated between endpoint and baseline.

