**PSA** 

PSA\_total\_BL (total PSA levels at baseline)
PSA\_total\_EP (total PSA levels at endpoint)
PSA\_total\_diff (difference in total PSA levels, endpoint-baseline)
PSA\_total\_diff\_cat (total PSA difference endpoint-baseline, decreased/unchanged=0, increased=1)

PSA\_ratio\_BL (PSA ratio free/total at baseline)
PSA\_ratio\_EP (PSA ratio free/total at endpoint)
PSA\_ratio\_diff (difference in total PSA levels, endpoint-baseline)
PSA\_ratio\_diff\_cat (PSA ratio diff endpoint-baseline, decreased/unchanged=0, increased=1))

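### Baseline PSA and T stage are not among the 24 listed covariates, so adjusting the Ki-67 models for them is not prespecified; the cost is modest precision in C1 and partial severity control in C2–C5

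*SAP*

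**What the plan says.** **Eligibility.** The SAP's Inclusion Criteria use three severity measures: "Patients with prostate cancer T1–T2, Gleason score <8, prostate-specific antigen (PSA) <20".

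**Baseline PSA.** Under Definition of secondary outcomes: "Levels of PSA are analyzed from blood samples taken at the inclusion meeting (baseline"). The PSA variable list defines `PSA_total_BL` as "total PSA levels at baseline". Its stated use is to form the endpoint-minus-baseline difference.

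**Candidate covariates.** The section "Covariates to test (possible confounding factors") lists 24 variables. Two describe disease before the intervention: `gleason_cat` ("categorized Gleason score at diagnosis") and `Biopsies_cancer` ("percent of biopsies with cancer at diagnosis"). Neither PSA nor T stage is listed.

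**How covariates are used.** Statistical Models says: "Difference between groups will be tested for variables stated below". Under Final model, inclusion is based on three considerations: being a known risk factor for the outcome (prior knowledge and causal diagrams), differing between exposure groups, and changing a coefficient by at least 10%.

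**Primary outcome.** Ki-67 is measured only in the prostatectomy specimen. It is defined as continuous (median, mean, maximum) and also dichotomised at the study median. The regression models are to report risk differences and relative risks.

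**The concern.** Ki-67 has no baseline value in this trial, so the outcome cannot be adjusted for its own starting level. Disease severity measured before randomisation is the natural substitute. The plan accepts this in part by listing Gleason score and percent positive biopsies at diagnosis, yet it leaves out two measures that it uses to admit men, and gives no reason.

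The consequence depends on the model:

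- **C1 (randomised group).** Baseline PSA and stage are balanced in expectation. Leaving them out costs precision and protection against chance imbalance.
- **C2–C5 (reported intake).** Intake is not randomised. If severity is related both to what men eat before surgery and to Ki-67, it confounds these models. The SAP does not state such a link, but by listing Gleason score and positive biopsies as possible confounders it treats severity as a candidate. The same reasoning reaches PSA and stage.

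The point concerns the Ki-67 models only, not baseline adjustment of the PSA outcomes.

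**Working it through.** **1. Count of the list.** There are 24 variables, and none is PSA or T stage. By name and description they divide as follows:

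- 7 are baseline or diagnosis variables: physical activity, percent positive biopsies, Gleason score at diagnosis, age, BMI group, smoking and heredity.
- 17 are measured at endpoint, during the intervention or at surgery. These include eleven dietary tertiles, and also Gleason score and tertiary grade at surgery, which cannot stand in for severity before randomisation.

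So 1 of the 3 eligibility measures is covered. Adding the other two would give 24 + 2 = 26 candidates and cover all three.

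**2. Availability.** PSA at inclusion is explicit. T stage is inferred from its role as an entry criterion; whether T1 and T2 are stored separately cannot be seen, because the variable list in Appendix 1 is not shown.

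**3. Size of the precision gain.** The SAP gives no power calculation, effect size, standard deviation or correlation with Ki-67, so there is no planned figure to reproduce. Let r be the assumed partial correlation of PSA and stage together with Ki-67, beyond the covariates already in the model.

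- Continuous Ki-67: residual variance is multiplied by 1 − r². Extra observations = 203 × (1/(1 − r²) − 1).
- Ki-67 split at the median, risk-difference scale, assuming bivariate normality: replace r² by r² × 2/π = 0.637 r².

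| Assumed r | Variance removed (continuous) | Extra observations, continuous | Variance removed (median split) | Extra observations, median split |
|---|---|---|---|---|
| 0.1 | 1% | 2 | 0.6% | 1 |
| 0.2 | 4% | 8 | 2.5% | 5 |
| 0.3 | 9% | 20 | 5.7% | 12 |
| 0.4 | 16% | 39 | 10.2% | 23 |

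Example for r = 0.3, continuous: 203 × (1/0.91 − 1) = 20.1. Median split: 0.637 × 0.09 = 0.0573, and 203 × (1/0.9427 − 1) = 12.3.

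**4. Cost side.** Each added degree of freedom costs roughly one observation. At r = 0.1, two added terms therefore about break even on continuous Ki-67 and gain nothing on the split outcome. The gain becomes visible from about r = 0.2.

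**5. Unit.** The 203 is stated in person moments, and the SAP does not say that these are 203 men. The table therefore counts observations.

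**The case against.** **A reader might infer that the models cannot adjust for PSA or stage.** The SAP does not say that. Its first rule for the final model admits known risk factors for the outcome and does not expressly confine the choice to the list. `PSA_total_BL` is a defined variable and could enter that way. What stands is narrower: nothing commits the analysis to it, group differences are tested only for listed variables, and the decision is left until later.

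**A reader might infer that both measures are on file for every man.** This is documented for PSA only. For T stage it is a reasonable inference without a named variable.

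**A reader might infer bias in the randomised comparison, or a large loss of power.** Neither is supported. Randomisation protects C1 from systematic bias. A large power gain would come from comparing a crude model with one holding a whole set of strong predictors. The relevant comparison is a model that already has Gleason score and positive biopsies against the same model plus PSA and stage. Eligibility also narrows the range of both measures ("Gleason score <8, prostate-specific antigen (PSA) <20", T1–T2), which tends to weaken their correlation with Ki-67. These objections stand, and they favour the low end of the table.

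**The list is a confounder list, and severity is already represented.** This is fair for C1. For C2–C5 it is the reason to include the missing measures: two severity variables control severity only in part. That severity influences diet is an assumption, not something the SAP states.

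**Conclusion.** The omission is real, and its consequences are limited. Adjustment of the Ki-67 models for baseline PSA and T stage is not prespecified. C1 remains unbiased and forgoes a small to modest amount of precision: about 2 to 39 observations on 203 for continuous Ki-67, or about 1 to 23 for the median split, with the lower values more plausible. In C2–C5 severity is controlled only through Gleason score and percent positive biopsies at diagnosis, and even these are candidates rather than fixed terms. The size of any residual confounding cannot be derived from the SAP.

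The figures rest on assumed partial correlations of 0.1 to 0.4, on 203 independent observations and, for the split outcome, on bivariate normality and a risk-difference model. A relative-risk model would give different values.

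**What to change.** In the SAP, name log(`PSA_total_BL`) as a prespecified baseline covariate in the adjusted Ki-67 models, beside `gleason_cat` and `Biopsies_cancer`. Add clinical T stage if T1 and T2 are recorded separately, and name its variable. If either is left out on purpose, give the reason. The same baseline terms should serve C1 and C2–C5, so that the randomised and intake analyses control severity alike.

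The cost is a short change of wording and one or two degrees of freedom. No new measurement is needed for PSA. For stage, the variable list should first be checked to confirm how it is stored. Whether the data-driven rules for the other covariates should also change is a separate question, and this fix does not depend on it.

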### STUDY DESIGN

The study design is shown in Figure 1. Men diagnosed with intermediate-risk prostate cancer T1–T2 (Gleason score <8, PSA <20), scheduled for radical prostatectomy, are identified at the Sahlgrenska University Hospital. Interested men are contacted by phone and a first meeting is scheduled. At the meeting the participants receive verbal and written information and sign an informed consent. A food frequency questionnaire including dietary and living habits and supplements are filled in and baseline blood samples are taken. The men are randomized to a diet or a control group through a closed envelop. All participants receive general dietary advice according to the Swedish National Food Agency (1). Participants are instructed to avoid supplements but no other dietary restrictions are given. The diet group receive a food package including food items high in phytoestrogens. Recipes and serving suggestions for the study diet are also given. The intake of the food items gradually steps up according to a schedule and the items are eaten in specific amounts until the surgery.

The participants are contacted by phone once during the study and a 24-hour recall is performed. The interview is made to control compliance in the study group and to estimate the intake of phytoestrogens in the control group. Near to surgery a similar food frequency questionnaire is filled in and endpoint blood samples are taken. Prostate biopsies are taken at the surgery. Hormones and PSA are analyzed from baseline and endpoint blood samples. The expression of androgen receptor and estrogen receptor alfa and beta are analyzed in tumor material. Tumor proliferation is calculated by ki-67 from prostatectomy specimens at surgery.

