### Analysis plan: PRODICA, [name]

values are calculated

Analyze of prostatectomy specimens from the surgery, variables: **ki67\_median** (median value of ki-67) **ki67\_mean** (mean value of ki-67) **ki67\_max** (max value of ki-67) Above variables will be dichotomized according to the median value in the study population:ki67\_median\_cat (0/1) ki67\_mean\_cat (0/1) ki67\_max\_cat (0/1)

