# **Definition of exposure**

The participants in the intervention group are defined as exposed and the participants in the control group are defined as not exposed.

**Group\_intervention** (0=control, 1=intervention)

Intake of different phytoestrogens at endpoint is based on information from the Food Frequency Questionnaire (FFQ) and the 24-h dietary recall.

**Phytoestogens\_EP\_3** (intake of phytoestrogens at endpoint divided in tertiles, calculated from the FFQ)

Lignans\_EP\_3 (intake of lignans at endpoint divided in tertiles, calculated from the FFQ)

Isoflavones\_EP\_3 (intake of isoflavones at endpoint divided in tertiles, calculated from the FFQ)

Coumestrol\_N58\_EP\_2 (dichotomized intake of coumesterol at endpoint, calculated from the FFQ)

Phyto\_24\_recall\_3 (intake of phytoestrogens at the 24-h dietary recall divided in tertiles)

The concentrations of phytoestrogens (daidzein, enterodiol, enterolactone, equol, genistein, glycetein,

Analysis plan: PRODICA, [name]
----------------------------	--------------

lariciresinol, and secoisolariciresinol) in plasma for a sub-group of participants:

**lignans\_EP\_nmol** (plasma levels of lignans at endpoint=enterolactone+ enterodiol+ lariciresinol+ seco\_EP\_nmol)

**lignans\_BL\_nmol** ((plasma levels of lignans at baseline=enterolactone+ enterodiol+ lariciresinol+ seco\_EP\_nmol)

**isoflavones\_EP\_nmol** (plasma levels of isoflavones at endpoint = daidzein\_EP\_nmol + genistein EP nmol + glycitein EP nmol + equol EP nmol)

**isoflavones\_BL\_nmol** (plasma levels of isoflavones at baseline = daidzein\_EP\_nmol + genistein\_EP\_nmol + glycitein\_EP\_nmol + equol\_EP\_nmol)

**phytoestrogens\_EP\_nmol** (plasma levels of total phytoestrogens at baseline = enterolactone\_EP\_nmol + enterodiol\_EP\_nmol + lariciresinol\_EP\_nmol + seco\_EP\_nmol + daidzein\_EP\_nmol + genistein\_EP\_nmol + glycitein\_EP\_nmol + equol\_EP\_nmol)

phytoestrogens\_BL\_nmol (plasma levels of total phytoestrogens at endpoint =
enterolactone\_BL\_nmol + enterodiol\_BL\_nmol + lariciresinol\_BL\_nmol + seco\_BL\_nmol +
daidzein\_BL\_nmol + genistein\_BL\_nmol + glycitein\_BL\_nmol + equol\_BL\_nmol)

lignans\_diff\_nmol = lignans\_EP\_nmol - lignans\_BL\_nmol

isoflav\_diff\_nmol= isoflavones\_EP\_nmol - isoflavones\_BL\_nmol

phyto\_diff\_nmol= phytoestrogens\_EP\_nmol - phytoestrogens\_BL\_nmol

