### PLANS FOR STATISTICAL ANALYZES

### VARIABLES TO ANALYZE

Created variables (for more details see attached variable list):

BMI (kg/m^2): BMI\_stata = Weight\_inclusion / ((Lenght\_inclusion/100) \* (Lenght\_inclusion/100) BMI\_group = 1= under weight (BMI <18.5); 2= normal weight (BMI 18.5-24.9); 3= Overweight (BMI 25-29.9); 4= Obese class (BMI 30-34.9) 1; 5= Obese class ≥2 (BMI ≥35)

Weight change (kg): Weight\_diff = Weight\_endpoint - Weight\_inclusion

Analysis plan: PRODICA, [name]	Version 2
---------------------------------------	-----------

Compliance (1= compliance >80; 0= compliance <80 %): Compliance 24 recall (based on reported intake of phytoestrogens at the 24-h dietary recall) Compliance intervention 24 r (based on eaten interventions foods reported from at the 24-h dietary recall) Compliance intervention (based on eaten interventions foods reported from at the end of the intervention) Intake of isoflavones (µg): Isoflavones BL = Genistein N56 BL + Daidzein N57 BL + Formononetin N59 BL + Biochanin N60 BL + Equol N75 BL Isoflavones EP = GenisteinN56 EP + Daidzein N57 EP + Formononetin N59 EP + Biochanin N60 EP + Equol N75 EP. Intake of lignans (µg): Lignans BL = SECOtot N61 BL + Matairesinol N62 BL Lariciresinol N71 BL + Pinoresinol N72 BL + Syringaresinol N73 BL + Medioresinol N74 BL + Enterodiol N76 BL + Enterolactone N77 BL Lignans EP=SECOtot N61 EP + Matairesinol N62 EP + Lariciresinol N71 EP + Pinoresinol N72 EP + Syringaresinol N73 EP + Medioresinol N74 EP + Enterodiol N76 EP + Enterolactone N77 EP Intake of phytoestrogens (ug): Phytoestogens BL = (Isoflavones BL + Lignans BL + Coumestrol N58 BL) Phytoestogens EP =(Isoflavones EP + Lignans EP + Coursetrol N58 EP) Level of physical activity: Physical activity BL group = low, moderate or high 1 = Low physical activity (101, 102, 103 or 201 points) 2 = Moderate physical activity (104, 202, 203, 301 or 302 points) 3 = High physical activity (204, 303, 304, 401, 402, 403 or 404 points) Intake of fatty fish: Fat fish group BL:  $0 \le 1$  times/month; 1 = 1-3 times/month;  $2 \ge 1$  times/week Fat fish group EP: 0 = <1 times/month; 1 = 1-3 times/month; 2 = >1 times/week Fat fish diff: Fat fish month EP - Fat fish month BL

Use of antibiotics:

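### The single-class models C3 to C5 cannot separate isoflavones, lignans and coumestrol if these are eaten together: an inactive class would show part of an active one's effect

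*SAP*

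**What the plan says.** Under Model building, the crude Ki-67 models are the randomised arm (C1), total phytoestrogen intake (C2), and then one class at a time: "C3: C0 + Isoflavones\_EP C4: C0 + Lignans\_EP C5: C0 + Coumestrol\_N58\_EP". The same pattern is repeated for total PSA, PSA ratio, estradiol, testosterone and the two hormone ratios. That makes seven outcomes and 7 × 3 = 21 single-class models; none holds two classes.

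The list headed "Covariates to test (possible confounding factors" has 24 entries covering diet, clinical, lifestyle and drug variables. Neither a phytoestrogen class nor the randomised arm is among them. A correlation rule accompanies the list: "If the correlation coefficient between two covariates in the model or between covariates and the main exposure are higher than 0.6", multicollinearity is considered and one of the covariates may be dropped. Covariates for the final model are chosen by three criteria. The first is "If a known risk factor for the outcome (based on previous subject matter knowledge and with the help of Directed Acyclic Graphs"; the others are a difference between exposure groups and a change of at least 10% in the coefficient.

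On the source of intake, STUDY DESIGN says: "The diet group receive a food package including food items high in phytoestrogens". VARIABLES TO ANALYZE defines the total as the sum of the three classes: "Phytoestogens EP =(Isoflavones EP + Lignans EP + Coursetrol N58 EP".

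**The concern.** C3 to C5 go beyond C2 only in looking at the classes separately, so readers will tend to use them to judge which class matters. The classes are components of one total, are measured by one questionnaire, and in the diet group may come from one package. If the package raises two classes, their intakes rise together. A model holding one of them then attributes to it part of whatever the other does.

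The covariate plan does not guard against this. A co-consumed class would probably meet the SAP's own criteria of differing between exposure groups and changing the coefficient by 10%, yet it is not listed as a candidate. If it were added, the 0.6 rule could lead to its removal exactly when the correlation, and so the bias, is largest. The class models are also repeated within genotype strata, so the ambiguity carries over. At stake are conclusions of the form that lignans, say, are associated with lower proliferation when only isoflavones are.

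**Working it through.** The SAP gives no between-class correlation, no class content of the package and no effect size. There is no stated figure to reproduce, and the size below rests on assumptions shown as a range.

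**Inputs from the SAP.** Isoflavones and lignans are defined in thirds, for example "Lignans\_EP\_3 (intake of lignans at endpoint divided in tertiles, calculated from the FFQ"; coumestrol is dichotomised. For Ki-67, "Above variables will be dichotomized according to the median value in the study population", so the overall risk is about 0.5. Confidence intervals are 95%. The planned size is 203 person moments, used here as the upper n, with n = 100 as the lower.

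**Assumptions.** Isoflavones have RD = -0.20 (top against bottom third, linear across thirds), lignans have no effect, and the latent intake correlation runs from 0 to 0.9. The model terms omit the tertile suffix used under Definition of exposure; tertile coding is assumed.

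**Step 1: expected bias.** Score the thirds T = 0, 1/2, 1. With lignans alone in the model, the expected coefficient is RD × Cov(T_iso, T_lig)/Var(T_lig) = RD × r_T, where r_T is the correlation of the two tertile scores. At latent r = 0.4, 0.6 and 0.8, r_T is 0.32, 0.50 and 0.69. The expected RD for the inactive class is therefore -0.20 × 0.32 = -0.064, -0.20 × 0.50 = -0.10 and -0.20 × 0.69 = -0.138.

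**Step 2: false-positive rate.** Var(T) = 1/6, so SE ≈ 0.5/√(n/6), which is 0.086 at n = 203 and 0.122 at n = 100. At latent r = 0.8 and n = 203, 0.138/0.086 ≈ 1.60, and the chance of |z| > 1.96 is about 36%. Simulation (linear probability model, robust standard errors, 3,000 runs per setting) gives:

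| Latent r | Share of RD -0.20 shown by inactive class | False positives, n = 203 | False positives, n = 100 |
|---|---|---|---|
| 0 | none | 5% | 6% |
| 0.2 | 16% | 7% | 6% |
| 0.4 | 34% | 11% | 9% |
| 0.6 | 49% | 20% | 12% |
| 0.8 | 69% | 36% | 20% |
| 0.9 | 81% | 46% | 26% |

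Repeat runs with other random numbers stay within about two percentage points. With both classes in one model, the inactive class's RD is within 0.004 of zero and its false-positive rate is about 5% to 7%.

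**Step 3: can the diet alone create the correlation?** Suppose 1:1 allocation, no correlation within arm, and a rise of d within-arm SD in both classes in the diet arm. The pooled correlation is (d²/4)/(1 + d²/4):
- d = 1: 0.25/1.25 = 0.20
- d = 2: 1/2 = 0.50
- d = 3: 2.25/3.25 = 0.69

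The inactive class then shows RD of about -0.03, -0.10 and -0.13.

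**Step 4: price of joint adjustment.** Take three equally correlated classes, d = 1.5 to 2.5 and within-arm correlation w = 0 to 0.8. The pooled correlation is r = (w + d²/4)/(1 + d²/4), from 0.36 to 0.92.
- Without arm, VIF = (1 + r)/[(1 - r)(1 + 2r)], about 1.2 to 8.7.
- With arm, VIF = (1 + d²/4)(1 + w)/[(1 - w)(1 + 2w)], about 1.6 to 8.9.

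**The case against.** The strongest reply is that these are secondary, descriptive models. Both hypotheses concern phytoestrogens as a whole, C1 rests on randomisation, and C2 uses the total. The one product term written out for the genotype interaction uses the arm. A marginal association by class is legitimate if reported as such, and the SAP nowhere says that C3 to C5 are meant to identify the active class. All of this stands and limits the point to class-specific conclusions.

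A reader might infer that an inactive class is credited with the whole of its companion's effect. The documents do not support that. The transfer is partial, vanishes at zero correlation, and depends on co-intake that the SAP does not quantify. It does not list the package's class content, so even a rise in more than one class is plausible rather than stated. A strong correlation among diet men is likewise assumed: foods eaten in set amounts leave less room for it, though varying compliance could produce it.

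A reader might also infer that the final model cannot adjust for another class. That goes too far. Selection draws on subject-matter knowledge and causal diagrams and is not expressly confined to the list, and the 0.6 rule is discretionary. Vegetable or fruit intake might also absorb some co-intake. What remains is that no class is named as a candidate and no joint model is planned.

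Finally, joint adjustment is not a complete cure. Questionnaire intakes carry error. With an assumed within-arm reliability of 0.5 to 0.7, the inactive class in a two-class joint model is still significant in about 7% to 14% of trials, or 6% to 11% with arm added. Forcing the arm in also removes the randomised contrast and leaves only observational variation within arms.

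**Conclusion.** The point holds in conditional form. As written, C3 to C5 and their counterparts cannot tell the classes apart if these are eaten together. The bias for an inactive class is roughly the correlation of the intake scores times the active class's effect. Under the stated assumptions (RD -0.20, latent correlation 0.4 to 0.8) that is about one third to 69% of the effect. A larger assumed RD of -0.30 raises the false-positive rate at n = 203 to about 20% to 65% over the same correlations. The actual size is unknown until the between-class correlations are seen. Class-specific conclusions are affected, including those within genotype strata; C1, C2 and the two hypotheses are not.

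**What to change.** Keep C1 to C5. Add one pre-specified model per outcome with Isoflavones_EP, Lignans_EP and Coumestrol_N58_EP together plus the selected confounders. Fit a version that also includes Group_intervention as a sensitivity analysis. In the text:

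- exempt the class terms from the 0.6 exclusion rule;
- report the between-class correlations overall and by arm;
- describe the single-class models as not separating the classes;
- make class-specific claims only from the joint model, and none if the classes prove too collinear to separate.

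This costs SAP wording and seven further models with their sensitivity versions, and needs no new data. The price is wider intervals for each class, which show how little the data may separate them. Because of questionnaire error, the joint model should be described as reducing the bias, not removing it.

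### One covariate-selection rule serves both the randomised arm and the intake exposures: it lets 17 post-randomisation variables into the arm models, and crude model C1 is given no precedence

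*SAP*

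**What the plan says.** Under Study design, men are randomised to diet or control. Hypothesis 1 contrasts adding the phytoestrogen-rich foods with not adding them. Definition of exposure makes the arm itself an exposure: "The participants in the intervention group are defined as exposed".

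Under Statistical models, one list of 24 candidate confounders serves all models. It includes "difference in weight between endpoint and baseline", "categorized Gleason score at surgery" and "intake of polyunsaturated fatty acids at endpoint, categorized in tertiles". Model building opens with "The association between intake of phytoestrogens and tumor proliferation will evaluated by regression models". The crude models follow: C1 has Ki-67 with Group_intervention, and C2 to C5 have Ki-67 with endpoint intakes. The same pattern is repeated for the PSA and hormone outcomes.

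A single Final model rule closes the section: "Which covariates included in the model will be based on" three criteria.

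1. The covariate is a known risk factor for the outcome, from subject knowledge and "with the help of Directed Acyclic Graphs".
2. "If differs between groups of exposure".
3. It changes the coefficient by 10% or more.

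The SAP does not say whether one criterion is enough or all are needed. It has no separate rule for Group_intervention. Intention-to-treat appears under Additional analysis, where it defines who is included and not which covariates are used.

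**The concern.** Randomisation removes confounding of the arm comparison except by chance. A variable that arises afterwards cannot confound it. It may instead be a consequence of the diet, either on the path to Ki-67 or sharing an unmeasured cause with it. Conditioning on the first kind removes part of the effect being tested. Conditioning on the second kind can produce an effect where there is none.

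Criteria 2 and 3 work in the wrong direction here. The intervention is a food package, so the endpoint intakes that differ between arms, and that shift the arm coefficient when added, are likely to be the ones the diet changed. The plan could therefore yield two arm estimates, C1 and the final model, that disagree, with no rule for which answers hypothesis 1.

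**Working it through.** **Step 1. Classify the 24 covariates by the timing in their labels.**

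| Timing | Covariates | Number |
|---|---|---|
| Baseline or diagnosis | physical activity at baseline, percent of biopsies with cancer, Gleason score at diagnosis, age, BMI group, smoking, heredity | 7 |
| Endpoint diet | energy, saturated fat, fatty fish, calcium, zinc, alcohol, monounsaturated fat, polyunsaturated fat, red meat, vegetables, fruit, vitamin E | 12 |
| Other post-randomisation | changed physical activity, weight change, Gleason score at surgery, tertiary Gleason grade at surgery, finasteride during the intervention | 5 |

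7 + 12 + 5 = 24, so 12 + 5 = 17 are recorded after randomisation. Finasteride is counted on timing alone, since nothing in the SAP suggests that the diet changes its use. Without it the count is 16.

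**Step 2. Look for a safeguard.** The correlation limit of 0.6 is about collinearity and ignores timing. With equal arms, a covariate shifted by d SD correlates with arm at d/√(d² + 4). For d = 0.8 this is 0.8/√4.64 = 0.37. Reaching 0.6 needs d = 1.5, because 1.5/√6.25 = 0.6. Large diet-induced shifts would pass.

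**Step 3. What criterion 2 selects by chance.** The SAP gives no threshold, so assume a 5% level and independent covariates. Among the 7 baseline covariates, P(at least one differs) = 1 − 0.95^7 = 0.30. Among the 17 others, with no diet effect on any of them, 17 × 0.05 = 0.85 are expected to differ, and P(at least one) = 1 − 0.95^17 = 0.58.

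**Step 4. Loss of a true effect (illustration).** Assumptions:
- the diagram excludes nothing;
- Ki-67 is split at the median, as the SAP plans, and analysed as a risk difference (RD), with a true RD of about −0.20;
- there are 100 or 203 men (the SAP gives 203 person moments, not men);
- 4 of the 12 diet variables, entered as tertiles, are shifted by 0.5 to 0.8 SD;
- covariates are independent, and criterion 2 uses the 5% level;
- 1,500 replicates per scenario.

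Mean RD, with criteria 2 and 3 read as either or both:

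| N | Mediated | Crude (C1) | Either | Both |
|---|---|---|---|---|
| 100 | 0% | −0.202 | −0.203 | −0.203 |
| 100 | 25% | −0.202 | −0.173 | −0.178 |
| 100 | 50% | −0.196 | −0.128 | −0.139 |
| 203 | 0% | −0.198 | −0.198 | −0.197 |
| 203 | 25% | −0.198 | −0.160 | −0.168 |
| 203 | 50% | −0.197 | −0.124 | −0.135 |

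Adjusting only for the seven baseline covariates gives −0.197 to −0.202 in all six scenarios (3,000 replicates). Of the 17, the rule selects on average 4.7 to 6.1 (either) or 1.5 to 2.1 (both). At a true RD of zero these become 9.1 to 10.1 and 2.8 to 3.4, because a 10% proportional change is easily reached when the coefficient is near zero.

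**Step 5. Creation of a false effect (illustration).** Take a true arm effect of zero and an endpoint covariate that the diet shifts by d SD. Within arms, it correlates r with the outcome through an unmeasured common cause. With unit variances, the adjusted arm coefficient has expectation 0 − r·d. For d = 0.25 and r = 0.2 this is −0.05 SD; for d = 1.0 and r = 0.4 it is −0.40 SD. Simulation with 200 men and 2,000 replicates gave −0.052 and −0.399. Over d = 0.25 to 1.0 and r = 0.2 to 0.4, the crude test rejected in 4% to 6% of replicates and the adjusted test in 7% to 78%.

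**The case against.** The strongest reply is that the list contains candidates only, and that a causal diagram drawn with the arm as exposure would exclude every mediator. That is correct, and the bias would then be zero. But the diagram appears only as an aid to identifying known risk factors for the outcome. Nothing says that it overrides the other two criteria, or that all three must be met.

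Second, unbiased comparisons are already planned: C1, the unadjusted group tests and an intention-to-treat analysis. That also stands, but none is named as the main result, and the adjusted model carries the label final. A protocol that is not shown might name the primary analysis; it would still have to be reconciled with this rule.

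Third, the model-building sentence speaks of intake, so the rule may have been meant for the intake models. There, endpoint diet is a defensible adjustment. However, the arm is defined as an exposure, and its crude models sit in the same blocks to which the rule applies.

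Fourth, 17 counts timing and not harm. Both arms receive the same general dietary advice, and the SAP does not show that the food package shifts calcium, alcohol or red meat. The number truly affected by the diet is unknown and may be well below 17.

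Fifth, the sizes are assumed. Nutrients from one questionnaire are not independent, so the selection counts are rough. With 25% mediation the shift is about 0.02 to 0.04, against a crude standard error, assuming equal arms with risks of 0.6 and 0.4, of √(4 × 0.24/100) = 0.10 or √(4 × 0.24/203) = 0.07. These points limit the claim about size, not the claim about the rule.

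**Conclusion.** The concern holds. As written, the rule can carry post-randomisation variables into the model for the randomised arm, and no text prevents it or puts C1 first. This must be fixed, because it governs the estimate that answers hypothesis 1.

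The bias in this trial cannot be computed from the SAP. It ranges from none, if the diagram removes all 17, to roughly a third of the effect in the 50% mediation scenario (from about −0.20 to −0.12 to −0.14). If covariate and outcome share an unmeasured cause, a false effect is also possible. Those sizes rest on the assumptions stated in the working. The count of 17, the missing precedence and the unstated way of combining the criteria rest on the text alone.

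**What to change.** - For the intention-to-treat Group_intervention models, name one main analysis in advance: either C1, or one version adjusted for a fixed list drawn from the seven baseline covariates (baseline questionnaire intakes may be added if wanted). State that it takes precedence over any other arm model.
- Remove selection by group difference and by 10% change for these models.
- Keep endpoint-diet covariates for the intake models (C2 to C5 and their counterparts), chosen by a causal diagram, and state that the diagram overrides the other two criteria.
- Treat the per-protocol analysis as a non-randomised comparison with its own covariate rule.
- Label any arm model that contains post-randomisation covariates as exploratory.

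The cost is SAP wording only, since the baseline variables are already collected. What is given up is the data-driven adjusted arm model as the final model. Precision may rise or fall, depending on how prognostic the dropped covariates are.
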